#### **Liver Function Parameters**

Liver function parameters of interest are total bilirubin (TBL), Alanine aminotransferase (ALT), Aspartate aminotransferase (AST) and alkaline phosphatase (ALP). The number (%) of subjects with worst post-baseline values as per Novartis Liver Toxicity guidelines will be summarized. The following summaries will be produced:

- ALT > 3xULN
- ALT > 5xULN
- ALT > 8xULN
- ALT > 10xULN
- ALT > 20xULN
- AST > 3xULN
- AST > 5xULN
- AST > 8xULN
- AST > 10xULN
- AST > 20xULN
- ALT or AST > 3xULN
- ALT or AST > 5xULN
- ALT or AST > 8xULN
- ALT or AST > 10xULN
- ALT or AST > 20xULN
- TBL > 2xULN
- TBL > 3xULN
- ALT or AST > 3xULN & TBL > 2xULN
- ALT or AST > 3xULN & TBL > 2xULN & ALP >= 2xULN
- ALT or AST > 3xULN & TBL > 2xULN & ALP < 2xULN

A figure displaying time course of hepatic function tests (ALT, AST, TBL, ALP) in subjects with Hy's law (ALT or AST > 3xULN & TBL > 2xULN & ALP < 2xULN) will be displayed in the Safety Set.

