Combined ^b AST or ALT and total bilirubin elevations	
Normal baseline ALT and AST and total bilirubin:	
AST or ALT > 3.0 x ULN with total bilirubin > 2.0 x ULN without evidence of cholestasis ^c OR	Permanently discontinue deferasirox.

Novartis	
Amended Protocol Version 01 (Clean))

Dose modifications for ICL670F2203		
In patients with elevated baseline AST or ALT or total bilirubin:	Repeat as soon as possible, preferably within 48 hours from awareness of abnormal results. Monitor LFTs ^a weekly or more frequently if clinically indicated until AST, ALT, or bilirubin resolve to baseline or stabilize	
[AST or ALT > 2x baseline AND > 3.0 x ULN] OR	over 4 weeks. Refer to Section 6.3.3.1 for additional follow-up evaluations as applicable.	
[AST or ALT > 8.0 x ULN], combined with [total bilirubin > 2x baseline AND > 2.0 x ULN]		
Hepatic Impairment		
Moderate hepatic impairment (Child-Pugh Class B)	Interrupt deferasirox and monitor patient. If liver disease prognosis improves, re-start deferasirox 7 mg/kg/day FCT or 50% of previous dose, whichever is less. Increase dose 3.5 mg/kg/day FCT every 2 weeks to a maximum of 50% of previous dose if the investigator determines that the dose increase is in the best interest of the patient.	
Severe hepatic impairment (Child-Pugh Class C)	Discontinue deferasirox.	
Skin and subcutaneous tissue disorders		
Severe skin reaction		
Severe skin reactions, including Stevens-Johnson	Deferasirox must be immediately discontinued and not reintroduced	
syndrome (SJS) and Toxic epidermal necrosis (TEN)		
Drug reaction with eosinophilia and systemic symptoms (DRESS)		
Skin rash (other than SJS)		
Mild/moderate severity (minimal symptoms which require no or minimal supportive treatment)	Continue study drug without dose adjustment. If the rash persists >1 week or becomes more severe, interrupt dosing. After the rash resolves, resume study drug at 50% of last dose. If the rash does not recur, increase dose to	
	100% of dose after 2 weeks.	
Severe rash (distressing symptoms requiring	Interrupt treatment until resolution of rash.	
interruption of study medication and/or systemic steroids)	After the rash resolves, resume at 50% dose. If necessary, a brief course of oral steroids may be given concurrently with resumption of study drug. If the rash does not recur, increase in steps of 3.5 mg/kg/day for deferasirox FCT every 2 weeks until last dose is achieved. If the rash recurs, discontinue study treatment.	
Other adverse events		

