"Combined" defined as total bilirubin increase to the defined threshold concurrently with ALI/ASI increase to the defined threshold		

If combined elevations of AST or ALT and total bilirubin do not meet the defined thresholds, please follow the instructions for isolated elevation of total bilirubin and isolated elevation of AST/ALT, and take conservative action based on the degree of the elevations (e.g. discontinue treatment at the situation when omit dose is needed for one parameter and discontinue treatment is required for another parameter). After all elevations resolve to the defined thresholds that allow treatment re-initiation, restart treatment either at the same dose or at one dose lower if criterion is met for dose reduction.

^{c.} "Cholestasis" defined as alkaline phosphatase elevation (> 2.0 x ULN and R < 2) in patients.

* Note: If total bilirubin > 3.0 x ULN is due to the indirect (non-conjugated) component only, and hemolysis as the etiology has been ruled out as per institutional guidelines (e.g., review of peripheral blood smear and haptoglobin determination), then \downarrow 1 dose and continue treatment at the discretion of the investigator.

** Note: anti-diarrheal medication is recommended at the first sign of abdominal cramping, loose stools or overt diarrhea.

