6.3.3.1 Follow up on potential drug-induced liver injury (DILI) cases

Increases in ALT and AST with an elevated total bilirubin can be seen in advanced stage HH, but is uncommon.

Increases in ALT and AST with an increased total bilirubin may be indicative of a potential DILI and should be considered as a clinically important event.

The threshold for potential DILI may depend on the patient's baseline AST/ALT and total bilirubin value; patients meeting any of the following criteria will require further follow-up as outlined below:

- Baseline normal ALT and AST and total bilirubin: AST or ALT > 3.0 x ULN combined with total bilirubin > 2.0 x ULN
- Elevated baseline AST or ALT or total bilirubin: [AST or ALT > 2 x baseline AND > 3.0 x ULN] OR [AST or ALT > 8.0 x ULN] combined with [total bilirubin > 2 x baseline AND > 2.0 x ULN]
- Normal ALT and AST with increased total bilirubin: rule out Gilbert's syndrome, defined by increased indirect bilirubin.

Medical review needs to ensure that liver test elevations are not caused by cholestasis, defined as alkaline phosphatase > 2.0 x ULN with R < 2 in patients.

Note: (R is calculated by ALT divided by alkaline phosphatase, using multiples of the ULN for both values. It denotes whether the relative pattern of ALT and/or alkaline phosphatase elevation is due to cholestatic ($R \le 2$), hepatocellular ($R \ge 5$), or mixed (R > 2 and < 5) liver injury.

In the absence of cholestasis, patients must immediately discontinue from study treatment and repeat LFTs as soon as possible, preferably within 48 hours from the awareness of abnormal results. Evaluation should include laboratory tests, detailed history, physical assessment and consideration of liver metastasis or new liver lesions, obstructions/compressions, etc.

1. Laboratory tests should include ALT, AST, albumin, creatinine kinase, total bilirubin, direct and indirect bilirubin, GGT, prothrombin time/INR and alkaline phosphatase.

Confidential

- 2. Collect detailed history, such as review of ethanol, concomitant medications, herbal remedies, supplement consumption, pre-existing liver conditions or risk factors.
- 3. Testing for acute hepatitis A, B, C or E infections and liver imaging (e.g. biliary tract) if warranted.
- 4. Additional testing for other hepatotropic viral infections (CMV, EBV or HSV), autoimmune hepatitis or consultation with a hepatologist for liver biopsy if clinically indicated.

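### The SAP's Hy's law figure and low-ALP row separate liver cases on ALP alone, so some cases that the protocol treats as potential drug-induced liver injury are not shown apart from cholestatic ones

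*SAP*

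**What the plan says.** **SAP 2.6.7, Liver Function Parameters.** The number of "subjects with worst post-baseline values as per Novartis Liver Toxicity guidelines will be summarized". Three rows combine transaminases with bilirubin. One has no ALP condition, one is "ALT or AST > 3xULN & TBL > 2xULN & ALP >= 2xULN", and one has the same elevations with ALP below 2 x ULN. A figure of liver tests over time is planned for subjects with Hy's "law (ALT or AST > 3xULN & TBL > 2xULN & ALP < 2xULN) will be displayed in the Safety Set". Only the figure carries the Hy's law name; the low-ALP row has the same condition without the name. R is not used in the SAP.

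**Protocol Table 6-2.** For patients with normal baseline values, permanent discontinuation follows "AST or ALT > 3.0 x ULN with total bilirubin > 2.0 x ULN without evidence of" cholestasis. Footnote c says cholestasis is "defined as alkaline phosphatase elevation (> 2.0 x ULN and R < 2) in patients".

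**Protocol 6.3.3.1.** Cholestasis is again "defined as alkaline phosphatase > 2.0 x ULN with R < 2 in patients", and "R is calculated by ALT divided by alkaline phosphatase, using multiples of the ULN for both values". The same note calls R from above 2 to below 5 mixed injury and R of 5 or more hepatocellular. Without cholestasis the patient stops study treatment. A case that is confirmed on repeat testing and has no other cause is reported as an SAE of potential drug-induced liver injury.

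**SAP section 4** lists COVID-19 analyses and ocular windows as changes from the protocol. It does not mention liver definitions.

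**The concern.** The protocol needs two conditions together before it sets a combined elevation aside as cholestatic. The SAP needs one. A patient with raised ALP but a much higher ALT meets the protocol's potential-DILI rule, yet falls on the cholestatic side of the SAP's split.

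At stake is how readable the liver display is. The figure is the one output that follows individual severe cases over time, and by construction it omits part of the group that the protocol singles out. In the ALP >= 2 x ULN row those patients are pooled with truly cholestatic ones. This matters more than usual because protocol 2.6 records transaminase elevations with deferasirox, both in the earlier dose-escalation study in hemochromatosis and after marketing.

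**Working it through.** The documents give no figure on this point to reproduce. The check applies both rules to illustrative profiles, which are assumptions and not trial data.

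**Inputs.** All values are multiples of ULN with a normal baseline. ALT is above 3 and bilirubin (TBL) above 2.
- Protocol: R = ALT / ALP; cholestasis if ALP > 2.0 and R < 2.
- SAP figure and low-ALP row: included if ALP < 2.

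| ALT | TBL | ALP | R | Protocol | SAP figure | Agree? |
|---|---|---|---|---|---|---|
| 3.5 | 2.5 | 1.5 | 2.33 | not cholestasis | in | yes |
| 3.5 | 2.5 | 2.5 | 1.40 | cholestasis | out | yes |
| 5.9 | 3 | 3 | 1.97 | cholestasis | out | yes |
| 6 | 2.5 | 2.5 | 2.40 | not cholestasis (mixed) | out | no |
| 8 | 3 | 2.5 | 3.20 | not cholestasis (mixed) | out | no |
| 8 | 3 | 3 | 2.67 | not cholestasis (mixed) | out | no |
| 12 | 4 | 2.2 | 5.45 | not cholestasis (hepatocellular) | out | no |
| 15 | 4 | 3 | 5.00 | not cholestasis (hepatocellular) | out | no |
| 3.5 | 2.5 | 2.0 | 1.75 | not cholestasis (ALP not above 2.0) | out | no |

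**Range of disagreement.** Let ALT be a x ULN. R > 2 means ALP < a/2. With ALP > 2 this requires a > 4, and the rules then disagree for ALP between 2 and a/2:
- a = 5: ALP 2 to 2.5
- a = 8: ALP 2 to 4
- a = 10: ALP 2 to 5
- a = 20: ALP 2 to 10

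The range widens as ALT rises.

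**Boundaries.** At ALP exactly 2.0 x ULN the rules disagree whatever R is, because the SAP's low-ALP group needs ALP below 2 and the protocol's cholestasis needs ALP above 2.0. This is the last line of the table. At R exactly 2 the protocol is not consistent with itself: the cholestasis definition uses R < 2, while the note on R counts R <= 2 as cholestatic.

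**Direction.** A case with ALP below 2 x ULN can never be protocol cholestasis. Taken alone, the ALP split can therefore only make the displayed group smaller than the group without protocol-defined cholestasis.

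**Scale of one case.** Assume the planned 100 deferasirox patients and one such case. The low-ALP row shows 0/100 (exact 95% CI 0 to 3.62%; upper limit 1 - 0.025^(1/100)) instead of 1/100 (0.03 to 5.45%). The row with no ALP condition shows 1/100 either way.

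**The case against.** A reader might infer that these patients drop out of the safety report, or that liver injury will be under-reported. The documents do not support that. Each such patient is counted in the row with no ALP condition and again in the ALP >= 2 x ULN row. SAP 2.6.7 lists all laboratory data, so R can be worked out by hand. Confirmed cases without another cause are SAEs, and SAP 2.6.3 tabulates and lists SAEs and events leading to discontinuation without regard to ALP.

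A reader might also infer that the SAP's Hy's law definition is an error. That is not shown either. The protocol sections on liver stopping and follow-up do not define Hy's law, the protocol's planned laboratory outputs (10.5.3.3) are shift tables and listings, and the SAP attributes its liver table to sponsor guidelines that are not in these documents. The table is an added descriptive screen.

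Three further limits stand:
- **Baseline.** The examples need a normal baseline. ALT just under 5 x ULN is eligible. With baseline ALT 4.5 x ULN, an ALT of 8 is neither above 2 x 4.5 = 9 nor above 8.0 x ULN, so the combined criterion is not met. With baseline bilirubin 1.5 x ULN, a value of 3 is not above 2 x 1.5 = 3.
- **Concurrency.** Table 6-2 requires the two elevations at the same time. The SAP uses worst post-baseline values and states no such rule, which could add cases. The net difference between the SAP and protocol groups is therefore not known.
- **Partial repair.** Adding R does not by itself make the two groups identical.

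What survives is narrower: no planned table or figure separates these cases from cholestatic ones, the figure leaves them out, and the SAP does not say that it uses a different definition.

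**Conclusion.** The mismatch is real and limited to one row and one figure. Assuming a normal baseline and concurrent elevations, cases with ALP above 2 x ULN and R above 2 meet the protocol's potential-DILI rule but are missing from the Hy's law figure and the ALP < 2 x ULN row. They include profiles that the protocol itself labels hepatocellular.

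How many patients this affects cannot be derived from the documents. It is expected to be small, since protocol 6.3.3.1 calls combined elevations uncommon in this disease. The analysis is descriptive, so no test or primary conclusion changes. It is a worthwhile, inexpensive improvement to the liver-safety display, and not evidence of lost or concealed cases.

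**What to change.** In SAP 2.6.7:
1. Keep the ALP < 2 x ULN row and the Hy's law label as they are.
2. Derive R from the ALT and ALP of the sample that meets the transaminase and bilirubin thresholds, not from peaks on different dates. State how a subject is handled when no single sample meets both.
3. Add one row: ALT or AST > 3 x ULN and TBL > 2 x ULN without protocol-defined cholestasis, that is, not (ALP > 2 x ULN and R < 2).
4. Include those subjects in the time-course figure, with a flag that distinguishes them from subjects meeting the conventional definition.
5. Record in SAP section 4 that two definitions are used, and why.

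The protocol's R < 2 and R <= 2 wordings must be reconciled so that the derived variable has one cut-off; this review takes no position on which applies. Concurrency and the baseline-relative criteria stay as separate differences, and the SAP should say so.

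The cost is one derived variable, one table row and a flag in a figure. ALT and ALP are already in the chemistry panel taken at every treatment visit. No new data are needed and no clinical rule is altered by the added outputs.

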#### 2.6.8 Vital Signs and Weight

Vital signs collected on treatment will be summarized. Values measured outside of on treatment period will be flagged in the listings.

For analysis of vital signs the clinically notable vital sign criteria are provided in Table 2-2 below and the windowing for vital signs are in Table 5-3.

Table 2-2 Definition of notable ranges for vital signs and weight

Parameter	Criteria for notable ranges
Systolic blood pressure	$\geq 180~mmHg$ / $\leq 90~mmHg$ with increase / decrease from baseline $\geq 20~mmHg$
Diastolic blood pressure	$\geq 105$ mmHg / $\leq 50$ mmHg with increase / decrease from baseline $\geq 15$ mmHg
Pulse rate	$\geq 120$ bpm / $\leq 50$ bpm with increase / decrease from baseline $\geq \!\! 15$ bpm
Weight	$\geq 10\%$ increase or decrease

The number and percentage of subjects with notable vital sign values (high/low) will be presented by treatment arm.

A listing of all vital sign assessments will be produced by treatment arm and notable values will be flagged. In the listing, the assessments collected outside of on-treatment period will be flagged.

#### 2.6.9 Other Safety Data

The number and percentage of subjects with clinically significant abnormalities in ECG test and auditory evaluation will be presented by treatment arm. A listing of all ECG and auditory assessments will be produced by treatment arm and the assessments collected during the posttreatment period will be flagged.

Results from pregnancy tests will be listed and positive results will be flagged.

# **3** Sample Size Calculation

The primary objective of the study is to estimate response rates and therefore the sample size is not based on power calculations. Sample size calculations were performed for the deferasirox FCT and phlebotomy arms to estimate the response rate with reasonable accuracy (half-width of 95% confidence interval).

Based on the Exjade study ICL670A2202, the subject dropout rate at month 6 (core study) is 24% and 12% at month 12 (optional extension phase). Assuming decreasing dropout rate over time and expected better subject compliance with deferasirox FCT formulation, a sample size of 100 subjects in the FCT arm is expected to have at least 60 subjects followed for 24 months to fulfil the FDA post-marketing requirement with regard to the ocular toxicity assessment in subjects receiving deferasirox.

With a sample size of 100 on deferasirox FCT and 50 subjects on phlebotomy, the projected half-widths of the 2-sided 95% confidence interval assuming various response rates are displayed in Table 3-1. The 95% confidence interval half-width extends at most to 0.096 and 0.136 in the deferasirox FCT and phlebotomy arms, respectively.

Novartis	Confidential	Page 31 of 36
SAP Amendment 1		Study No. CICL670F2203

Response rate (RR)	Half-width of the 95% CI for deferasirox FCT	Half-width of the 95% CI for phlebotomy
0.60	N=100	N=50
0.60	0.096	0.136
0.65	0.093	0.132
0.70	0.090	0.127
0.75	0.085	0.120
0.80	0.078	0.111
0.85	0.070	0.099
0.90	0.059	0.083

Table 3-1 Half-width of 95% CI of response rates in deferasirox FCT and phlebotomy arms

#### 4 Change to protocol specified analyses

Additional analysis related to COVID-19 related AEs and COVID-19 specific protocol deviations (Section 2.2.1 and Section 2.6.3) added. Due to COVID-19, the scheduled assessments had delays and consequently the subjects' assessments were unscheduled. Therefore, the Ocular windowing for the scheduled assessments was updated (see details in Section 5.3.2).

# 5 Appendix

# 5.1 Imputation Rules

#### 5.1.1 Study Treatment

The following rule should be used for the imputation of date of last administration:

Scenario 1: If the date of last administration is completely missing and there is no EOT eCRF page, the subject is considered as on-going. The subject should be treated as on-going, and the cut-off date should be used as the last dosing date.

Scenario 2: If the date of last administration is completely or partially missing and the EOT eCRF page is available (prior to any death date or withdrawal of consent date, if available):

Case 1: The date of last administration is completely missing, and the EOT visit date is complete, then this latter date should be used.

Case 2: Only Year(yyyy) of the dose end date is available and yyyy < the year of EOT date:

#### Use Dec31yyyy

Case 3: Only Year(yyyy) of the dose end date is available and yyyy = the year of EOT date:

#### Use EOT date

Case 4: Both Year(yyyy) and Month (mm) are available for the date of last administration, and yyyy = the year of EOT date and mm < the month of EOT visit:

Use last day of the Month (mm).

Novartis	Confidential	Page 32 of 36
SAP Amendment 1		Study No. CICL670F2203

After imputation, compare the imputed date with the start date of that specific record, if the imputed date is < start date of that record

#### Use the start date of that record.

Subjects with missing start dates are to be considered missing for all study treatment component related calculations and no imputation will be made. If the date of first administration is missing, then the date of last administration should not be imputed.

There will be no attempt to impute any other date from eCRF ZQ page.

#### 5.1.2 AE, Concomitant medications and safety assessment date Imputation

#### Table 5-1 Imputation of start dates (AE, CM) and assessments (LB, EG, VS)

Missing Element	Rule
day, month, and year	• No imputation will be done for completely missing dates
day, month	
 
If available year = year of study treatment start date then         
 
If stop date contains a full date and stop date is earlier than study treatment start date then set start date = 01JanYYYY >                 
 
Else set start date = study treatment start date.
 
 
 
If available year > year of study treatment start date then 01JanYYYY
 
If available year < year of study treatment start date then 01JulYYYY
 
 
 

day	
 
If available month and year = month and year of study treatment start date then         
 
If stop date contains a full date and stop date is earlier than study treatment start date then set start date= 01MONYYYY.
 
Else set start date = study treatment start date.
 
 
 
If available month and year > month and year of study treatment start date then 01MONYYYY
 
If available month and year < month year of study treatment start date then 15MONYYYY
 

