# Data Included in the Analysis

Data from all subjects who signed informed consent will be used in the analysis. All statistical analyses described hereafter will be performed using all data collected in the database up to the final database lock date. The final database lock date will be established after all randomized

Novartis	Confidential	Page 12 of 36
SAP Amendment 1		Study No. CICL670F2203

subjects have completed 24 months of treatment including safety follow-up if applicable, or have discontinued from the study (see Protocol Section 4.3 for more details).

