#### Baseline

Baseline is considered as the result of an investigation describing the 'true' uninfluenced state of the subject.

For **efficacy evaluations**, (e.g. serum ferritin), the last available assessment before or on the date of randomization is taken as 'baseline' value or 'baseline' assessment.

For **safety evaluations** (e.g. laboratory, vital signs, ocular etc.) the last available assessment before or on the date of start of study treatment is taken as 'baseline' value or 'baseline' assessment.

If subjects have no value as defined above, the baseline result will be missing.

If an assessment is planned to be performed prior to the first administration of study treatment in the protocol and the assessment is performed on the same day as the first administration of study treatment, it will be assumed that it was performed prior to study treatment administration if assessment timepoint is not collected or is missing. Unscheduled assessments will be considered in the determination of baseline.

Subjects who start treatment and discontinue from the study on the same day may have 2 different sets of data collected on study Day 1, one being reported to the Day 1 visit, the other reported to the EOT visit. Data reported at the EOT visit are not eligible for baseline selection.

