#### Table 5-2Imputation of end dates (AE, CM)

Missing Element	Rule (*=last treatment date plus <30> days not > (death date, cut-off date, withdrawal of consent date))
day, month, and year	Completely missing end dates (incl. ongoing events) will be imputed by the end date of the on-treatment period*
day, month	If partial end date contains year only, set end date = earliest of 31DecYYYY or end date of the on-treatment period *
day	If partial end date contains month and year, set end date = earliest of last day of the month or end date of the on-treatment period*

Any AEs and ConMeds with partial/missing dates will be displayed as such in the data listings. Any AEs and ConMeds which are continuing as per data cut-off will be shown as 'ongoing' rather than the end date provided.

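### Three SAP date-imputation rules give wrong baselines, AE end dates or exposure for the few records they catch (minor)

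*SAP*

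**What the plan says.** **Assessment dates.** SAP 5.1.2, Table 5-1, is titled "Imputation of start dates (AE, CM) and assessments (LB, EG, VS". It deals with a record whose day is missing in the month of treatment start, or whose day and month are missing in the year of treatment start. Unless a full stop date falls before treatment start, the instruction is "Else set start date = study treatment start date". Partial dates in a later month or year go to the first of that month or to 1 January.

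**Baseline.** For safety data, SAP 2.1.1 says that "the last available assessment before or on the date of start of study treatment is taken as 'baseline' value". It adds: "Unscheduled assessments will be considered in the determination of baseline".

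**AE end dates.** SAP Table 5-2 states: "Completely missing end dates (incl. ongoing events) will be imputed by the end date of the on-treatment period". That period ends 30 days after last treatment, or earlier at death, cut-off or consent withdrawal. Partial end dates are also held to no later than that day.

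**Last dose.** SAP 5.1.1 Scenario 1 covers a patient whose date of last administration is completely missing and who has no EOT page: "The subject should be treated as on-going, and the cut-off date should be used as the last dosing date".

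**Timing.** The single analysis is at final lock. SAP 2.1 says: "The final database lock date will be established after all randomized" subjects have either finished 24 months of treatment, with safety follow-up where applicable, or left the study.

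**The concern.** Moving an uncertain AE start date to Day 1 is cautious, because the event then counts as treatment-emergent. Moving a laboratory, ECG or vital-sign record to Day 1 works the other way, because an on-treatment value can enter the reference against which later change is judged. Two criteria in SAP Table 2-1 depend directly on that reference: creatinine more than 33% above baseline, and ALT or AST more than twice baseline.

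The end-date rule assumes that every AE starts on treatment. The SAP does not: section 2.5.2 repeats the ocular AE analysis over the on-treatment and post-treatment periods, 2.6.3 lists AE duration, and 2.6.6 counts occurrences by the gap between one AE's end and the next AE's start.

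Scenario 1 suits an interim cut with patients still on treatment. At a final lock it can only lengthen exposure, and with it the on-treatment window, for anyone it catches.

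**Working it through.** The plan states no figure for this point, so there is none to reproduce. The rules were applied as written to assumed dates.

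**1. Assessments (Table 5-1 with the 2.1.1 baseline).** Assume treatment starts on 5 March 2019. A laboratory, ECG or vital-sign record has one date and no stop date, so the default branch always applies in the start month or start year.

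| True date (study day) | Recorded as | Imputed date | Eligible as baseline |
|---|---|---|---|
| 19 Mar 2019 (15) | Mar 2019 | 5 Mar 2019 (Day 1) | yes |
| 1 Sep 2019 (181) | 2019 | 5 Mar 2019 (Day 1) | yes |
| 2 Apr 2019 (29) | Apr 2019 | 1 Apr 2019 (Day 28) | no |
| 1 Feb 2020 (334) | 2020 | 1 Jan 2020 (Day 303) | no |

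How often a partial date would be moved, given that one exists, is calendar arithmetic over a 365-day year:
- Day missing, sample 14 days after start: (365 − 12 × 14)/365 = 54% fall in the start month. At 28 days: (365 − 12 × 28)/365 = 8%.
- Day and month missing: (365 − 14)/365 = 96% at 14 days, (365 − 28)/365 = 92% at 28 days, (365 − 168)/365 = 54% at 168 days.

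These shares are conditional on a partial date and are not rates of harm.

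Effect on the creatinine criterion, with assumed values: true Day 1 value 80, on-treatment value 100 moved to Day 1, later confirmed value 110 µmol/L (taken to exceed ULN).
- True baseline: 110/80 − 1 = 37.5%, above 33%.
- Same-day values averaged, as SAP 5.3.1 does within its windows: baseline (80 + 100)/2 = 90, and 110/90 − 1 = 22.2%.
- Moved value used alone: 110/100 − 1 = 10%.

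In the last two cases the notable criterion is missed.

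**2. AE end dates (Table 5-2).** Duration = end − start + 1, the form the SAP uses for exposure; it gives no separate formula for AE duration. On-treatment end = last treatment + 30 days.
- Last treatment 1 Jun 2020, on-treatment end 1 Jul 2020. An ongoing AE starting 2 Jul 2020 gets −1 + 1 = 0 days.
- Same patient, AE starting 15 Sep 2020: −76 + 1 = −75 days.
- Last treatment 1 Dec 2019, on-treatment end 31 Dec 2019, AE starting 30 Nov 2020: −335 + 1 = −334 days.

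A partial end date in the month or year of these starts gives the same result. SAP 5.1.1 already has the missing safeguard for the last-dose date: an imputed date earlier than the record's start is replaced by that start. Table 5-2 has no such line. Applying it would set each example to 1 day.

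**3. Scenario 1.** Exposure = last − first + 1. The planned maximum is 104 × 7 = 728 days (protocol 6.1.5). Assume first dose 5 Mar 2019, true last dose 10 Jun 2019 (98 days), no last-administration date and no EOT page. The SAP defines no cut-off date. It is taken here as the last patient's month 24 plus 30 days, with accrual continuing E months after this patient: exposure = (24 + E) × 30.4375, rounded, + 30 + 1.

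| E (months, assumed) | Imputed exposure (days) |
|---|---|
| 6 | 944 |
| 12 | 1127 |
| 24 | 1492 |
| 36 | 1857 |

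All exceed 728, and the on-treatment window lengthens with them. If an EOT page with a complete visit date exists, Scenario 2 Case 1 ends exposure at that date.

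**The case against.** **Scenario 1 should rarely apply.** A reader might infer that any lost patient is counted as on drug until the cut-off. The text does not say so. Both the last-administration date and the EOT page must be absent, and protocol 7.1.8 requires lost patients to be recorded on a Disposition eCRF. Protocol 9.4 has missing values queried before lock. This stands: the rule catches only unresolved data failures. It remains wrong for those.

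**A moved assessment does not automatically become baseline.** Blood tests, vital signs and weight are scheduled on Day 1, so the moved record competes with a true Day 1 value, and section 2.1.1 gives no tie-break. This also stands, but it leaves the result ambiguous rather than safe, since averaging or replacement are both possible. The same-day convention that opens "If an assessment is planned to be performed prior to the first administration of study treatment in the protocol" does not rescue a Week 2 sample. It covers only assessments planned before dosing, while the before-or-on definition has no such limit.

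**Partial dates are probably rare for laboratory samples.** A central laboratory handles nearly all specimens (protocol 7.2.2.6). That is a fair judgement, although no rate is given. SAP 2.6.7 pools local results, and the rule also covers ECGs and vital signs recorded at sites.

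**The end-date rule barely reaches any table.** AE incidence depends on start dates. Listings show partial dates as recorded and continuing events as ongoing. The SAP does not say whether listed duration uses the imputed end date. Routine AE collection is scheduled to 30 days after last dose, which limits post-treatment AEs. It does not exclude them: both treatments are interrupted at SF ≤ 100 µg/L, so last treatment can fall well before the EOT visit, and ocular follow-up can run to month 24.

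**Conclusion.** The three rules give wrong results as written, but for few records. Severity is minor.

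- **Table 5-1:** on-treatment assessments with a partial date in the start month or start year become eligible as baseline. Later partial dates stay post-baseline. The possible harm is a missed notable creatinine or ALT/AST value.
- **Table 5-2:** an AE starting after the on-treatment period can be given an end before its start. This can affect listed duration and the one-day-gap occurrence counts. A reader might infer that ocular AE incidence, the key secondary endpoint, is distorted; it is not, because events are classified by start date.
- **Scenario 1:** exposure and the on-treatment window can exceed 104 weeks for a patient with neither a last-administration date nor an EOT page.

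The primary response rate is not affected. This takes serum ferritin to lie outside Table 5-1, since 5.1.2 is headed for safety assessments and 2.1.1 treats ferritin as an efficacy measure with its own baseline tied to randomization. All dates, creatinine values and accrual spans above are assumptions.

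**What to change.** 1. **Baseline.** State in 2.1.1 that an assessment with an imputed date cannot serve as baseline unless its recorded visit is Screening or Day 1. Keep the date-based windows otherwise; windowing by visit label would leave unscheduled samples without a rule. An on-treatment record dated to Day 1 would then fall in no post-baseline window (Week 2 begins at Study Day 2), so state that it still counts in worst-value tables.
2. **Table 5-2.** Apply the on-treatment cap only to AEs that start in the on-treatment period, and add the floor already used in 5.1.1: an imputed end date is never before the record's start date.
3. **Scenario 1.** Replace the cut-off date with the last date on which the patient is documented as on treatment, not later than Week 104.

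The cost is a few SAP sentences and matching program changes before lock. No new data are needed.
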